#### **9.1.5. Study Files and Retention of Records**

The investigator must maintain adequate and accurate records to enable the conduct of the study to be fully documented and the study data to be subsequently verified. These documents should be classified into at least the following 2 categories: (1) investigator's study file and (2) participant clinical source documents.

The investigator's study file will contain the protocol/amendments, eCRFs, IRB/IEC, and governmental approval with correspondence, the ICF(s), drug records, staff curriculum vitae and authorization forms, and other appropriate documents and correspondence.

The required source data should include sequential notes containing at least the following information for each participant:

- Participant identification
- Documentation that participant meets eligibility criteria (ie, medical history, physical examination, and confirmation of diagnosis [to support inclusion and exclusion criteria])
- Documentation of the reason(s) a consented participant is not enrolled
- Participation in study (including study number)

- Study discussed and date of informed consent
- Dates of all visits
- Documentation that protocol-specific procedures were performed
- Results of efficacy parameters, as required by the protocol
- Start and end date (including dose regimen) of study drug, including dates of dispensing and return
- Record of all AEs and other safety parameters (start and end date; causality and severity) and documentation that adequate medical care has been provided for any AE
- Concomitant medication (start and end date; dose if relevant; dose changes)
- Date of study completion and reason for early discontinuation, if it occurs

All clinical study documents must be retained by the investigator for at least 2 years or according to local laws, whichever is longer, after the last approval of a marketing application in an ICH region (ie, the United States, Europe, or Japan) and until there are no pending or planned marketing applications in an International Council for Harmonisation region; or, if no application is filed or if the application is not approved for such indication, for 2 years after the investigation is discontinued and regulatory authorities have been notified. Investigators may be required to retain documents longer if specified by regulatory requirements, by local regulations, or by an agreement with Gilead. The investigator must notify Gilead before destroying any clinical study records.

Should the investigator wish to assign the study records to another party or move them to another location, Gilead must be notified in advance.

If the investigator cannot provide for this archiving requirement at the investigational site for any or all of the documents, special arrangements must be made between the investigator and Gilead to store these records securely away from the site so that they can be returned sealed to the investigator in case of an inspection. When source documents are required for the continued care of the participant, appropriate copies should be made for storage away from the site.

#### **9.1.6. Case Report Forms**

An eCRF casebook will be completed by an authorized study personnel member whose training for this function is completed in the electronic data capture (EDC) system unless otherwise directed. The eCRF casebook will only capture the data required per the protocol schedule of events and procedures, unless collected by a nonelectronic data capture vendor system (eg, central laboratory). The Inclusion/Exclusion Criteria and Enrollment eCRFs should be completed only after all data related to eligibility are available. Data entry should be performed in accordance with the CRF Completion Guidelines provided by the sponsor. Subsequent to data entry, a study monitor may perform source data verification. System-generated or manual queries will be issued in the EDC system as data discrepancies are identified by the study monitor or

Gilead personnel who routinely review the data for completeness, correctness, and consistency. The site investigator, site coordinator, or other designee is responsible for responding to the queries in a timely manner, within the system, either by confirming the data as correct or updating the original entry, and providing the reason for the update (eg, data entry error). Original entries as well as any changes to data fields will be stored in the audit trail of the system. Regular oversight by the principal investigator of the data entered into the EDC system is expected to occur on an ongoing basis throughout the study to ensure quality and completeness. At a minimum, before any interim, final, or other time points (as instructed by Gilead), the investigator will apply his/her electronic signature to confirm that the forms have been reviewed and that the entries accurately reflect the information in the source documents. At the conclusion of the study, Gilead will provide the site investigator with a read-only archive copy of the data entered. This archive must be stored in accordance with the records retention requirements outlined in Section 9.1.5.

#### **9.1.7. Investigator Inspections**

The investigator will make available all source documents and other records for this study to Gilead's appointed study monitors, to IRB/IEC, or to regulatory authority or health authority inspectors.

#### **9.1.8. Protocol Compliance**

The investigator is responsible for ensuring the study is conducted in accordance with the procedures and evaluations described in this protocol.

### **9.2. Sponsor Responsibilities**

#### **9.2.1. Protocol Modifications**

Protocol modifications, except those intended to reduce immediate risk to study participants, may be made only by Gilead. The investigator must submit all protocol modifications to the IRB in accordance with local requirements and receive documented IRB approval before modifications can be implemented.

#### **9.2.2. Study Reports and Publications**

A clinical study report (CSR) will be prepared and provided to the regulatory agency(ies) when applicable and in accordance with local regulatory requirements. Gilead will ensure that the report meets the standards set out in the ICH Guideline for Structure and Content of Clinical Study Reports (ICH E3). Note that an abbreviated report may be prepared in certain cases. For studies with sites in countries following the EU Regulation No. 536/2014, a CSR will be submitted within 1 year (6 months for pediatric studies, in accordance with Regulation [EC] No. 1901/2006) after the global end of study (as defined in Section 3.4).

Investigators in this study may communicate, orally present, or publish study data in scientific journals or other scholarly media in accordance with the Gilead clinical study agreement.

### **9.3. Joint Investigator/Sponsor Responsibilities**

#### **9.3.1. Regulatory and Ethical Considerations**

This study will be conducted in accordance with the protocol and the following:

- The ethical principles of the Declaration of Helsinki
- International Council for Harmonisation (ICH) Good Clinical Practice (GCP)
- Applicable laws and regulatory requirements

#### **9.3.2. Payment Reporting**

Investigators and their study personnel may be asked to provide services performed under this protocol (eg, attendance at investigator meetings). If required under the applicable statutory and regulatory requirements, Gilead will capture and disclose to federal and state agencies any expenses paid or reimbursed for such services, including any clinical study payments, meal and/or travel expenses or reimbursements, consulting fees, and any other transfer of value.

#### **9.3.3. Access to Information for Monitoring**

In accordance with regulations and guidelines, the study monitor must have direct access to the investigator's source documentation and any participant records in order to verify the adherence to the protocol and the accuracy of the data recorded in the eCRF. The study monitor is responsible for routine review of the case report form/eCRF form at regular intervals throughout the study to verify adherence to the protocol and the completeness, consistency, and accuracy of the data being entered on them. The investigator agrees to cooperate with the study monitor to ensure that any problems detected through any type of monitoring (central, off-site, on-site) are resolved.

#### **9.3.4. Access to Information for Auditing or Inspections**

Representatives of regulatory authorities or Gilead may conduct inspections or audits of the clinical study. If the investigator is notified of an inspection by a regulatory authority, the investigator agrees to notify the Gilead study monitor immediately. The investigator agrees to provide to representatives of a regulatory agency or Gilead access to records, facilities, and personnel for the effective conduct of any inspection or audit.

#### **9.3.5. Study Discontinuation**

Gilead reserves the right to terminate the study at any time, and the investigator has the right to terminate the study at his or her site. Should this be necessary, both parties will arrange discontinuation procedures and notify the participants, appropriate regulatory authority(ies), and IRB/IEC. In terminating the study, Gilead and the investigator will ensure that adequate consideration is given to the protection of the participants' interests.

## 11.2. Marketing Authorization Status of Study Interventions

Study Intervention Name	Category	Authorized in ≥ 1 Country Following EU Regulation No. 536/2014	Authorized in ≥ 1 ICH Country
bictegravir 50 mg/emtricitabine 200 mg/tenofovir alafenamide 25 mg fixed-dose combination tablets	Study drug	Yes	Yes

EU = European Union, ICH = International Council for Harmonisation

### 11.3. Study Procedures Table

**Table 3. Study Procedures Table**

Study Procedures	Screening	Day 1 b	Week 4 c	Week 12 c	Week 24 c	30-Day Follow-up d	ESDD e	Notes
Informed Consent	X							
Medical History	X							
Concomitant Medications	X	X	X	X	X	X	X	At screening, concomitant medications taken within 30 days prior to screening will be recorded; at subsequent visits all medications since the last study visit will be recorded.
Adverse Events	X	X	X	X	X	X	X	
Complete Physical Examination	X							Complete physical examination (urogenital/anorectal examinations will be performed at the discretion of the investigator).
Symptom-Directed Physical Examination		X	X	X	X	X		Symptom-directed physical examination at all post-screening time points.
Vital Signs and Weight	X	X	X	X	X	X	X	
Height	X							
Urinalysis	X	X	X	X	X	X	X	
Urine Pregnancy		X	X	X	X	X	X	For participants of childbearing potential only
Serum Pregnancy	X							For participants of childbearing potential only
Chemistry Profile f	X	X	X	X	X	X	X	
Hematology Profile	X	X	X	X	X	X	X	CBC with differential and platelet count
CD4+ Cell Count	X	X		X	X		X	
Plasma HIV-1 RNA g	X	X	X	X	X	X	X	
HBV and HCV Serologies h	X							
Estimated GFR	X	X		X	X		X	Estimated GFR according to the Cockcroft-Gault formula for creatinine clearance
Metabolic Assessments i		X		X	X			
Baseline PK, Sparse PK: trough and postdose PK sample j		X	X	X	X			

Study Procedures	Screening	Day 1 b	Week 4 c	Week 12 c	Week 24 c	30-Day Follow-up d	ESDD e	Notes
Plasma Storage Sample		X	X	X	X		X	For optional future research
Whole Blood sample for potential HIV DNA genotyping		X						Whole blood sample for virology analysis
Plasma HIV-1 genotyping/phenotyping sample k			X	X	X		X	HIV-1 genotype/phenotype resistance testing for participants with unconfirmed virologic rebound with HIV-1 RNA value $\geq 200$ copies/mL
Dried Blood Spot (DBS) collection			X	X	X		X	TFV-DP from DBS will be run in retrospect for participants with confirmed viral failure.
HIVTSQs		X		X	X			
HIVTSc Questionnaire			X					
Additional study specific questions		X	X					
Qualitative interview			X					Qualitative interview will explore in-depth experiences on CAB+RPV, reasons for switch B/F/TAF and satisfaction post switch. The visit window for the interview is from Week 3 to Week 9.
Study Drug Accountability		X	X	X	X	X	X	
Study Drug Dispensation		X		X				
Observed Dosing		X	X	X				Participants must take their study drug in the clinic for observed dosing on Day 1, Week 4, and Week 12.

CBC = complete blood count; CD4+ = clusters of differentiation 4; DNA = deoxyribonucleic acid; DBS = dried blood spot; ESDD = early study drug discontinuation; GFR = glomerular filtration rate calculated using the Cockcroft-Gault equation; HBV = hepatitis B virus; HCV = hepatitis C virus; HIV-1 = human immunodeficiency virus type 1; HIVTSQs = HIV treatment satisfaction status questionnaire [quantitative]; HIVTSQc = HIV treatment satisfaction change questionnaire [quantitative]; RNA = Ribonucleic acid; PK = pharmacokinetic(s); TFV-DP = tenofovir diphosphate.

- a Evaluations to be completed within 42 days prior to Day 1 visit.
- b Participants will be dispensed study drug at the Day 1 visit; initiation of treatment with the study drug must take place in the clinic for observed dosing at Day 1 visit.
- c All study visits are to be scheduled relative to the Day 1 visit date. Visit windows are  $\pm 2$  days of the protocol-specified date through Week 12,  $\pm 6$  days of the protocol-specified date for Week 24. For the purpose of scheduling a 30-day follow-up visit, a  $\pm 6$ -day window may be used. Those participants who prematurely discontinue study drug and continue in the study through at least one subsequent visit after the early study drug discontinuation visit will not be required to complete the 30-day follow-up visit.
- d Only applies to participants who miss the Week 24 visit, and must be completed within 30 days of discontinuing study drug.
- e Early study drug discontinuation visit to occur within 72 hours of last dose of study drug.
- f Chemistry profile: alkaline phosphatase, AST, ALT, total bilirubin, direct and indirect bilirubin, total protein, albumin, bicarbonate, BUN, calcium, chloride, creatinine, glucose, potassium, and sodium.
- g For any post-Day -1 visit, if the HIV-1 RNA value is  $\geq 50$  copies/mL, a retest should be performed at a scheduled or unscheduled visit 2-4 weeks after the date of the original test.

- h Hepatitis B virus surface Antigen (HBsAg), Hepatitis B core antibody (HBcAb), and Hepatitis C virus (HCV) serologies (reflex HCV RNA is performed in participants with positive HCV Ab serology)
- i Metabolic Assessments: Fasting lipid panel (total cholesterol, HDL, direct LDL, triglycerides). If the participant has not fasted prior to the visit, the visit may proceed, but the participant must return within 72 hours in a fasted state.\
- j A single PK plasma sample will be collected at Day 1 prior to dose. A single trough plasma PK sample approximately 23 to 24 hours after the previous B/F/TAF dose and prior to B/F/TAF dosing on Weeks 4, 12, and 24, and a single postdose plasma PK sample at approximately 2 hours post B/F/TAF dose, witnessed by the study staff, at Weeks 4, 12, and 24 will be collected
- k HIV-1 genotype/phenotype resistance testing (which includes protease, reverse transcriptase, and integrase testing) only conducted for participants with confirmed virologic failure with HIV-1 RNA value  $\geq$  50 copies/mL. Participants should be managed according to [Figure 2](#). Following virologic rebound, participants will be asked to return to the clinic (2-4 weeks later) prior to the next scheduled visit or at the next scheduled study visit, for an HIV-1 RNA and HIV-1 genotype and phenotype blood draw. Based on the results of this testing, participants should be managed according to the Virologic Rebound Schema ([Figure 2](#)). Participants with HIV-1 RNA  $\geq$  50 copies/mL at Week 12 and/or 24 will be asked to return for an unscheduled visit within the visit window for a retest. Participants with HIV-1 RNA  $\geq$  200 copies/mL at ESDD, last visit, or Week 12 or 24 will also have resistance testing conducted.

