### **6.3. Instructions for Study Procedures**

#### **6.3.1. Adverse Events**

From the time informed consent is obtained through the first administration of study drug, record all SAEs, as well as any AEs related to protocol-required procedures, on the AE electronic case report form (eCRF). All other untoward medical occurrences observed during the screening period, including exacerbation or changes in medical history, are to be considered medical history. After study drug administration, report all AEs and SAEs. See Section [7](#) for additional details.

Evaluation for AEs will occur at the times shown in [Table 3](#).

In case new (nonprohibited) therapies need to be administered during the study, the benefit-risk to the participant should be carefully assessed and consideration given to the timing of any necessary introduction of new therapies.

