#### 6.4.1.1. Participants with HIV-1 RNA $\geq 50$ copies/mL at last on-treatment study visit or at Study Endpoints

Participants with HIV-1 RNA  $\geq 50$  copies/mL at ESDD or last visit will be considered virologic failures. Participants with HIV-1 RNA  $\geq 50$  copies/mL at Week 12 or Week 24 will be asked to return for an unscheduled visit within the visit window for a retest.

Participants with HIV-1 RNA  $\geq 200$  copies/mL at ESDD or last visit will also have resistance testing conducted.

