#### **7.3.2.       Adverse Events**

Following initiation of study drug, collect all AEs, regardless of cause or relationship, until 30 days after administration of the last dose of study drug and report the AEs on the eCRFs as instructed.

All AEs and clinically significant laboratory abnormalities should be followed until resolution or until the AE is stable, if possible. Gilead may request that certain AEs be followed beyond the protocol-defined follow-up period.

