#### **7.3.3.       Serious Adverse Events**

All SAEs, regardless of cause or relationship, that occur after the participant first consents to participate in the study (ie, signing the ICF) and throughout the duration of the study, including the 30-day follow-up visit, must be reported on the applicable eCRFs and to Patient Safety (PS) as instructed below in this section. This also includes any SAEs resulting from protocol-associated procedures performed after the ICF is signed.

Any SAEs and deaths that occur after the posttreatment follow-up visit but within 30 days of the last dose of study drug, regardless of causality, should also be reported.

Investigators are not obligated to actively seek SAEs after the protocol-defined follow-up period; however, if the investigator learns of any SAEs that occur after the protocol-defined follow-up period has concluded and the event is deemed relevant to the use of study drug, the investigator should promptly document and report the event to PS.

Instructions for reporting SAEs are described in Section [7.4.1](#).

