#### **7.7. Toxicity Management**

Treatment-emergent toxicities will be noted by the investigator and brought to the attention of the Gilead medical monitor (or designee) for treatment related Grade 3-4 AEs or SAE, who will have a discussion with the investigator and decide the appropriate course of action. Whether or not considered treatment related, all participants experiencing AEs must be monitored periodically until symptoms subside, any abnormal laboratory values have resolved or returned to Day -1 levels or they are considered irreversible, or until there is a satisfactory explanation for the changes observed.

Clinical and laboratory AEs should be managed as outlined in Section 3.3 and Appendix 11.6.

Any questions regarding toxicity management should be directed to the Gilead medical monitor (or designee).

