CBC = complete blood count; CD4+ = clusters of differentiation 4; DNA = deoxyribonucleic acid; DBS = dried blood spot; ESDD = early study drug discontinuation; GFR = glomerular filtration rate calculated using the Cockcroft-Gault equation; HBV = hepatitis B virus; HCV = hepatitis C virus; HIV-1 = human immunodeficiency virus type 1; HIVTSQs = HIV treatment satisfaction status questionnaire [quantitative]; HIVTSQc = HIV treatment satisfaction change questionnaire [quantitative]; RNA = Ribonucleic acid; PK = pharmacokinetic(s); TFV-DP = tenofovir diphosphate.

a Evaluations to be completed within 42 days prior to Day 1 visit.

b Participants will be dispensed study drug at the Day 1 visit; initiation of treatment with the study drug must take place in the clinic for observed dosing at Day 1 visit.

c All study visits are to be scheduled relative to the Day 1 visit date. Visit windows are \pm 2 days of the protocol-specified date through Week 12, \pm 6 days of the protocol-specified date for Week 24. For the purpose of scheduling a 30-day follow-up visit, a \pm 6-day window may be used. Those participants who prematurely discontinue study drug and continue in the study through at least one subsequent visit after the early study drug discontinuation visit will not be required to complete the 30-day follow-up visit.

d Only applies to participants who miss the Week 24 visit and must be completed within 30 days of discontinuing study drug.

e Early study drug discontinuation visit to occur within 72 hours of last dose of study drug.

f Chemistry profile: alkaline phosphatase, AST, ALT, total bilirubin, direct and indirect bilirubin, total protein, albumin, bicarbonate, BUN, calcium, chloride, creatinine, glucose, potassium, and sodium.

- g For any post-Day -1 visit, if the HIV-1 RNA value is ≥ 50 copies/mL, a retest should be performed at a scheduled or unscheduled visit 2-4 weeks after the date of the original test.
- h Hepatitis B virus surface Antigen (HBsAg), Hepatitis B core antibody (HBcAb), and Hepatitis C virus (HCV) serologies (reflex HCV RNA is performed in participants with positive HCV Ab serology)
- i Metabolic Assessments: Fasting lipid panel (total cholesterol, HDL, direct LDL, triglycerides). If the participant has not fasted prior to the visit, the visit may proceed, but the participant must return within 72 hours in a fasted state.

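### Participants who attend Week 24 have no scheduled contact in the 30 days after last dose, although AEs, SAEs and pregnancies are still reportable then and the whole-study AE tables count that period

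*Protocol*

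**What the plan says.** **Collection.** Protocol 7.3.2 has sites collect all AEs "until 30 days after administration of the last dose of study drug". Protocol 7.3.3 requires SAE reporting "throughout the duration of the study, including the 30-day follow-up visit". It adds that SAEs and deaths after that visit but still within 30 days of last dose should also be reported.

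**Counting.** Protocol 8.6 and 8.6.2 and SAP 7 and 7.2.6.1 all run to last dose plus 30 days. SAP 7.2.7.1 cuts its Week 12 AE tables at the nominal Week 12 visit. It equates the whole study period with through Week 24 and gives no corresponding Week 24 cut.

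**Schedule.** Protocol 6.3.1 states: "Evaluation for AEs will occur at the times shown in" Table 3. That table marks AEs and urine pregnancy at the 30-day follow-up, but footnote d limits the visit: "Only applies to participants who miss the Week 24 visit, and must be completed within 30 days of discontinuing study drug". SAP Appendix 1 repeats it: "Only applies to participants who miss the Week 24 visit and must be completed within 30 days of discontinuing study drug". Protocol 6.6 mentions the visit only for early discontinuers who are then withdrawn from the study.

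**Contacts that remain.** Protocol 7.3.2: "All AEs and clinically significant laboratory abnormalities should be followed until resolution or until the AE is stable, if possible". Protocol 7.7: "all participants experiencing AEs must be monitored periodically until symptoms subside". Under Protocol 6.4.1.1, a participant with HIV-1 RNA of 50 copies/mL or more at Week 24 "will be asked to return for an unscheduled visit within the visit window for a retest".

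**Pregnancy.** Appendix 11.5 runs required contraception to the 30-day follow-up visit. Item 5 of the same appendix describes participant notification with a limit of 4 days after last dose. Section 7.4.2.3 keeps a separate reporting duty on the investigator through post-treatment follow-up.

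**The concern.** The collection and counting windows extend 30 days past last dose for everyone, but the visit that would serve those 30 days is not given to completers. For a completer with nothing open at Week 24, a new event in that month is recorded only if the participant volunteers it or the site makes contact on its own initiative. The resulting tables look like full coverage of the window, and nothing in the SAP tells the reader otherwise. The tables affected include Grade 3 or 4 drug-related AEs through Week 24, which SAP 7.1 lists as a secondary safety endpoint.

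There is also a practical gap. A participant of childbearing potential who completes the study has no defined date on which required contraception ends.

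**Working it through.** The plan gives no figure to reproduce, because the question is whether the schedule covers the counting window. The check sets the two side by side and measures the uncovered days.

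**Inputs**
- Dosing from Day 1 to the end of Week 24, nominal Day 168 (Protocol 5.4; SAP Table 3-1).
- Treatment-emergent window ends at last dose + 30 days (Protocol 8.6.2; SAP 7.2.6.1).
- Week 24 visit window of ±6 days (Table 3, footnote c).
- Last scheduled AE evaluation for a completer is the Week 24 visit (Protocol 6.3.1; Table 3, footnote d).

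**Formula.** Uncovered share = (last-dose day + 30 − Week 24 visit day) / (last-dose day + 30).

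**Last dose on the visit day**
- Day 168: 30 / (168 + 30) = 30/198 = 15.2%.
- Day 162: 30 / (162 + 30) = 30/192 = 15.6%.
- Day 174: 30 / (174 + 30) = 30/204 = 14.7%.

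**Last dose on Day 168, visit moving within its window**
- Visit on Day 174: (198 − 174)/198 = 24/198 = 12.1%.
- Visit on Day 162: (198 − 162)/198 = 36/198 = 18.2%.

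The second set is the fairer range, because the documents do not fix last dose to the visit day. Same-day dosing is plausible for North American participants, who give a witnessed post-dose PK sample at Week 24. It is not established for the roughly 10 French participants, who have no PK sampling.

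These are shares of calendar days, not of events. The documents give no completion rate, no AE rate by time, and no share of participants with something open at Week 24, so the number of missed events cannot be estimated.

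**With a contact at last dose + 30 days.** Taking last dose and visit both on Day 168, scheduled coverage rises from 168/198 (84.8%) to 198/198.

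**Participants who miss Week 24.** Their visit must fall within 30 days of stopping, so it can come well before day 30. Footnote c waives it for early discontinuers who attend at least one visit after the early-discontinuation visit. Their coverage of the window may therefore be incomplete too.

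**The case against.** The strongest case on the other side has five parts.

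1. **The duty to report does not lapse.** A reader might infer that events after Week 24 are not collected, or that sites stop asking. The documents do not support that. Section 7.3.2 applies to everyone until day 30, and 7.3.3 expects SAE and death reports even after the last visit. Volunteered events would be recorded and counted. What stands is only the absence of a scheduled contact.

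2. **Some completers will be seen again.** Open AEs, clinically significant laboratory abnormalities and HIV-1 RNA retests all generate contact. That is true, but none of these is a scheduled enquiry about new events, and they do not reach a participant with nothing open.

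3. **The pregnancy text is ambiguous.** A reader might infer that participants are told to stop notifying pregnancies 4 days after last dose. Item 5 of 11.5 can be read that way. It can equally describe when the pregnancy begins, in which case one conceived on drug and recognised on day 20 must still be notified. The investigator's duty in 7.4.2.3 stands on either reading. The wording needs clarifying; it is not proof of a notification gap.

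4. **Footnote d looks deliberate.** It is explicit and identical in substance in both documents, and some completers may stay on commercial B/F/TAF, which weakens the case for a post-treatment check. Both are fair. Neither explains why the collection window, the tables and the contraception rule still assume follow-up to day 30.

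5. **Little depends on it.** The study has one arm, the analysis is descriptive, the drug is approved, and the co-primary endpoints end at Week 12. This stands, and it sets the weight of the point.

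**Conclusion.** The mismatch is real on the current text of both documents. Completers have no scheduled contact for new-onset AEs, SAEs or pregnancy during 30 days that the whole-study AE tables count. The uncovered share is about 15% of eligible days, or 12.1% to 18.2% if last dose is Day 168 and the visit falls 6 days later or earlier. The consequence is possible under-ascertainment of unknown size in tables labelled through Week 24.

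A reader might infer more than this. The Week 12 co-primary endpoints are not touched for completers, whose uncovered days all come after Week 24. With a single arm, no treatment comparison is biased. The gap is not exclusive to completers either, since coverage may also be incomplete for those who miss Week 24. Pregnancy is not itself an AE and the SAP only lists it, so that part concerns safety follow-up and clear instructions, not the AE tables.

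The conclusion rests on reading Table 3 as the full schedule of AE evaluations, as Protocol 6.3.1 says it is. It merits a low-cost improvement, not a major correction.

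**What to change.** **If follow-up is still possible.** Add one brief telephone contact by existing site staff about 30 days after last dose, covering AEs, SAEs and pregnancy, for every participant without a later visit. In Appendix 11.5, set both the end of required contraception and the end of participant pregnancy notification at 30 days after last dose. The cost is at most about 35 short calls and a protocol amendment with IRB/IEC approval.

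**If follow-up has ended.** SAP 1.2.1 describes visits in the past tense, so the calls may no longer be possible. In that case keep every reported event in the tables. Cutting completers' tables at the Week 24 visit would match the Week 12 rule, but it would discard reported AEs and SAEs and depart from Protocol 8.6 and 8.6.2. Instead, state two things in the SAP and the report: that the AE tables labelled through Week 24 include events to last dose plus 30 days, and that completers had no scheduled contact after Week 24. SAP Section 1 says the SAP is finalised before the database is, so the statement can be added there at almost no cost.
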